We will conduct the study within clinics from three diverse systems. A majority of participants will be recruited from Kaiser Permanente Northern California (KPNC), an integrated healthcare delivery system with more than 3.5 million members, 20 hospitals, and over 50 outpatient clinics. KPNC has over 6600 adult members with diagnoses of Autism Spectrum Disorder (ASD). The KPNC team will select 4 intervention clinics and 4 matched control clinics to participate in the study and can select additional clinics if we do not meet anticipated recruitment goals. Seventeen KPNC clinics each have >100 adult patients with diagnosed ASD. Kaiser's great resources and commitment make it an optimal site both for this pilot study and for a future large RCT. However, we recognize that Kaiser's strengths as an integrated health system can limit generalizability. As such, we will also study a variety of additional clinics in Oregon to proactively develop an implementation plan that can be effective in diverse practices. We will work with two clinics from Legacy Health System, a private, non-profit hospital system with 6 hospitals and 26 primary care clinics. Though each of the Legacy primary care clinics has only about two-dozen adult patients with diagnosed ASD, we feel it's important to study the implementation of the toolkit in a private health system with low prevalence of diagnosed ASD, as that may be more typical. Finally we will use two of the four primary care clinics run by the Oregon Health and Science University (OHSU) Department of Family Medicine. We chose these two clinics because they represent diverse practices – the Gabriel Park Clinic is in an urban area and the Scappoose Clinic is a rural health center in a town of under 7000 people. The two clinics have a total of approximately 200 adult autistic patients. Though the two sites are so different that they cannot serve as controls for one another, they each consist of 4 "pods" that function independently, with their own group of providers, front and back office staff, and patient panels. As such, we will use two pods as the intervention site and two pods as the control site for each of the OHSU clinics. All three participating health systems use Epic as their electronic medical record (EMR).

Overview, Study Design and Change Model:

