Provider Surveys: We are acutely aware of the importance of minimizing the burden of this study on PCPs, both in the current study and in the future R01. As such, we will use patient surveys and administrative data to answer most of our research questions, and will only conduct in-depth interviews with 3 providers from each intervention site (N=15). However, we believe that provider self-efficacy may be an important mechanism of action that needs to be assessed directly from all providers. We will conduct an extremely brief survey (<5 minutes) at baseline and at the end of the study with all providers who have autistic patients in their panels (N 50-80). Providers may participate via email, fax, telephone, or online. The survey will include items on self-efficacy and attitudes toward autistic adults. Follow-up surveys will also include an item about whether they are aware of the AASPIRE Healthcare Toolkit and, if so, a few items about their satisfaction with the toolkit.

Administrative Data: We will use administrative data from each health system to assess healthcare utilization. Obtaining such information is relatively straightforward for a closed healthcare system such as Kaiser. However, it is more complex in non-integrated systems. We will explore how well we can capture data from the OHSU and Legacy Systems using EMR data, including Care Everywhere (an Epic System that links EMR visits from most local health systems) and claims data from Health Share (the Medicaid managed care coordinated care plan for our county). Though this study will not be powered to show a difference in unmet needs or healthcare utilization, these data can help inform the future R01. It will also give us experience working with this type of administrative data from each health system.

Quantitative Data Analysis

Our quantitative analysis plan includes descriptive and psychometric analyses, assessment of missing data and attrition, and a mixed effects regression analysis to compare results from intervention and control sites while adjusting for demographic and disability-related characteristics. We will conduct analyses using STATA 14 (Statacorp, College Station, Texas). We will use an intention-to-treat approach for all analyses.

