Power Considerations: We plan to enroll 250 participants to have complete follow-up data on at least 200 (100 intervention;100 control), which will allow us to detect an effect size of 0.4 with a power of 80% using an independent sample t-test test with a two-tailed hypothesis and an alpha of 0.05. It would provide 97% power to detect an effect size of 0.5. Though one must use caution in deriving effect sizes from small pilots, based on our preliminary results, we feel it is reasonable to expect this level of change in our short-term outcomes. For example, we noted a 0.55 effect size in the number of barriers to healthcare. We are using a conservative estimation to compensate for the complex multivariate analyses proposed in Aims 2 and 3.

Qualitative Interviews with Patients, Providers, Staff, and Administrators

Participants and Sampling: We will collect qualitative data from 30 patients, 15 providers, and 15 administrators/staff selected from the 5 intervention sites to better understand the implementation process and the tool's potential impact. We will use maximum variation sampling,⁵⁸ a purposive sampling strategy which increases depth of understanding by selecting a diverse group of individuals who are expected to have different perspectives. We will use data from our quantitative surveys to identify which patient and supporter participants to invite to the qualitative study. The goal will be to create a patient sample that has wide distribution of the following characteristics: 1) gender; 2) age, 3) race/ethnicity, 4) living situation, 5) need for assistance to receive healthcare, 6) use of alternative and augmentative communication (AAC), 7) permission (yes/no) to share AHAT report with provider, and 8) clinic site. We will primarily recruit participants who have seen their PCP after using the Toolkit, as they are the ones most likely to provide rich, interesting information. However, we will intentionally sample 5 participants who did not see their PCP to try to understand potential barriers to care that were not addressed by the toolkit. We will recruit patient participants for an interview between 4-8 months after they complete the baseline survey. We will use a similar strategy to obtain a varied sample of providers and administrators/staff from each of the clinics, purposely sampling people who serve in a variety of roles in each clinic. Participants will receive an additional \$50 stipend for participating in an interview.

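### The 80% power at effect size 0.4 ignores that arms are whole sites and has no reserve; the 97% at 0.5 should be 94%; and the number of sites is given as both 5+5 and 7+7

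*Combined protocol and SAP*

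**What the plan says.** Power Considerations (under Quantitative Data Analysis) plans to enrol 250 in order to have at least 200 completers, 100 per arm, "which will allow us to detect an effect size of 0.4 with a power of 80% using an independent sample t-test test", two-tailed with alpha 0.05. It continues: "It would provide 97% power to detect an effect size of 0.5". The only allowance it names is this: "We are using a conservative estimation to compensate for the complex multivariate analyses proposed in Aims 2 and 3".

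Arms are formed from sites, not individuals. Under Setting, "The KPNC team will select 4 intervention clinics and 4 matched control clinics to participate in the study"; two Legacy clinics take part; and for the OHSU clinics, "we will use two pods as the intervention site and two pods as the control site for each of the OHSU clinics". Protection of Human Participants divides the KPNC and Legacy clinics half and half, describes the same OHSU pod arrangement, and totals the sites at 7 intervention and 7 control.

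Other sections give a different count:

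- Overview, Study Design and Change Model has 5 intervention and 5 control sites, 10 in all.
- Provider Surveys says the study "will only conduct in-depth interviews with 3 providers from each intervention site (N=15"), which implies 5 sites.
- The qualitative sampling plan draws "30 patients, 15 providers, and 15 administrators/staff selected from the 5 intervention sites".

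On analysis, the opening of Quantitative Data Analysis promises "a mixed effects regression analysis to compare results from intervention and control sites". The Aim 2 paragraph that follows describes multivariate linear or logistic regression of the 6-month change, with study arm as predictor plus covariates. It names no random effect.

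**The concern.** Patients in one clinic share providers, staff and the clinic's own implementation protocol, so their changes over six months may be correlated. If so, 100 completers in a handful of sites carry less information than 100 independent people, and a calculation that treats them as independent overstates power. The named allowance concerns multivariate modelling, not clustering.

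Two further problems need no assumption. The power quoted at 0.5 does not follow from the stated inputs, and the number of sites, which any cluster-adjusted calculation needs, is contradictory.

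The consequences are that a null Aim 2 result could be over-read, and that a future cluster-randomised trial would be planned from a pilot whose site unit is undefined and which has no stated plan to report an ICC. Because the outcome is a change score, only between-site differences in change matter. Stable differences in level between sites cancel.

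**Working it through.** **Inputs from Power Considerations:** 100 completers per arm, standardised effect d = 0.4 or 0.5, two-sided alpha 0.05, independent-sample t-test.

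**Step 1: reproduce the stated figures.** Power comes from the noncentral t with 198 df and noncentrality d × √(100/2).

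- d = 0.4: noncentrality 2.83, power 80.4%. The stated 80% reproduces.
- d = 0.5: noncentrality 3.54, power 94.0%. The stated 97% does not reproduce; it would need 119 per arm.

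Two alternative readings reach about 97% at 0.5, but neither also gives 80% at 0.4:

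| Reading | Power at 0.5 | Power at 0.4 |
|---|---|---|
| Stated: two-sided, 100 per arm | 94.0% | 80.4% |
| One-sided, 100 per arm | 97.0% | 88.0% |
| Two-sided, all 250 enrolled (125 per arm) | 97.6% | 88.3% |

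The source of the 97% cannot be determined from the document.

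**Step 2: reserve.** At 99 per arm the power at 0.4 is 79.97%. The 80% point lies at an effective 99.1 per arm.

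**Step 3: count the sites.** From Setting and Protection of Human Participants: KPNC 4+4, Legacy 1+1, OHSU 2+2, total 7+7. The Overview, Provider Surveys and qualitative sampling text give 5+5. Three providers per site is 15 at 5 sites but 3 × 7 = 21 at 7 sites.

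**Step 4: effect of clustering.** The document gives no ICC, so 0.01, 0.02 and 0.05 are assumptions. The effective n per arm is the sum over sites of m / (1 + (m − 1) × ICC), where m is completers per site. For example, 7+7 equal sites have m = 100/7 = 14.3; at ICC 0.01 the design effect is 1 + 13.3 × 0.01 = 1.133, and 100/1.133 = 88.3. The unequal case assumes sizes 19, 19, 19, 19, 4, 10 and 10. All rows use 198 df and give no credit for matching or covariates. Entries are for ICC 0.01 / 0.02 / 0.05.

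| Sites | Effective n per arm | Power at 0.4 | Effect detectable at 80% power |
|---|---|---|---|
| 7+7 equal | 88.3 / 79.0 / 60.1 | 75 / 71 / 59% | 0.42 / 0.45 / 0.51 |
| 7+7 unequal | 86.6 / 76.6 / 57.3 | 75 / 69 / 57% | 0.43 / 0.46 / 0.53 |
| 5+5 equal (m = 20) | 84.0 / 72.5 / 51.3 | 73 / 67 / 52% | 0.43 / 0.47 / 0.56 |

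Power at 0.5 becomes 91 / 88 / 78% (7+7 equal) or 90 / 85 / 71% (5+5). Power at 0.4 drops below 80% at an ICC of 0.0007 (7+7 equal), 0.0006 (7+7 unequal) or 0.0005 (5+5).

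**Step 5: cluster degrees of freedom.** With df equal to the number of sites minus 2, power at 0.4 is 69 / 64 / 52% (7+7 equal, 12 df) or 62 / 56 / 43% (5+5, 8 df). Part of this is the df convention alone: at ICC 0 the figures are already 74% and 70%.

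**Step 6: what matching could recover.** Suppose sites are analysed in pairs and each pair shares a fraction s of the site variance. The variance of a pair difference is 2 × [ICC × (1 − s) + (1 − ICC)/m]. For 7+7 equal sites with 198 df, power at 0.4 is 78 / 76 / 69% at s = 0.5 and 80 / 79 / 77% at s = 0.8. At s = 1 there is no loss. The values of s are assumptions.

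**The case against.** The 80% sentence is arithmetically correct for the test it names, and the clustering loss rests entirely on ICCs the document does not supply. The KPNC control clinics are matched and the Aim 2 model adjusts for a list of covariates, either of which could offset the loss. If covariates explained an assumed 10% of variance, power at 0.4 (7+7 equal sites, 198 df) would be 79.6% at ICC 0.01; at an assumed 20% it would be 84.1% at ICC 0.01 and 79.9% at ICC 0.02. The targets of 200 completers and 250 enrolled are floors, and clinics can be added. The planning effect of 0.4 sits below the pilot's 0.55 for barriers. A mixed effects regression is already named, so the missing random effect can be read as a gap in detail. And this is a non-randomised pilot.

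Much of this stands as qualification. The clustering loss is conditional, and a properly specified mixed model would protect the Aim 2 inference. But a mixed model does not change the power statement. At ICC 0.05 the same covariate assumptions leave power at 63% to 68%. Only the KPNC clinics are called matched, and no pairing term is described. Choosing 0.4 over 0.55 is a margin on effect size and does not make 80% at 0.4 right; the pilot's other short-term outcome, communication, showed only 0.26. Floors and optional clinics are not part of the stated calculation. None of this touches the 97% or the site count: the 7+7 describes the starting set, so permission to add sites does not explain the difference.

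**Conclusion.** The point holds and should be fixed. Two parts rest on no assumption: power at 0.5 under the stated test is 94.0%, not 97%, and the current text gives both 5+5 and 7+7 sites.

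The third part is certain in kind and conditional in size. The 80% at 0.4 assumes independence, no clustering allowance is stated, and essentially no participants are spare. Over assumed ICCs of 0.01 to 0.05, power is 75% down to 59% with 7+7 equal sites and 73% down to 52% with 5+5, lower still with cluster degrees of freedom, and higher if matching or covariates absorb site or residual variance. The Aim 2 inference is not shown to be invalid, provided the mixed effects model is used with a site term.

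**What to change.** 1. In Power Considerations, change 97% to 94% and label it as assuming independence.
2. Reconcile the site count across the Setting, Overview, Provider Surveys, qualitative sampling and Protection of Human Participants sections, and define the site unit at OHSU.
3. Restate the power at 0.4, or the detectable effect, over an ICC range labelled as an assumption, with the number and expected sizes of sites. Alternatively, state that the 80% ignores clustering.
4. Carry the mixed effects model into the Aim 2 paragraph with a random effect for the allocated site, treat the plain t-tests on outcomes as descriptive, and report the estimated ICC with its interval for planning the later trial.

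Pairing terms, health system as a fixed effect and pod-level units are options to consider, not corrections.

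The cost is protocol and SAP wording and a less favourable stated power. These changes require no additional patients, sites or data.

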170 autistic adults participated in the study, either independently or with support. Participants had a wide range of disability-related characteristics (e.g. approximately 1/3 required assistance to receive healthcare always or often, 1/3 required it sometimes, and 1/3 rarely or never; approximately half lived in their own place and half with family or in a group home). Almost all patient participants (>94%) felt that the AHAT and the toolkit were easy to use, important, and useful. A majority (65%) of participants gave permission for us to mail their AHAT report to their PCP. Of the thirty-five participants who answered an open-ended item about why they chose not to have their report sent, a majority indicating that they planned on bringing the report to the PCP themselves (N=8), were in the process of changing or did not have PCP (N=8), or did not need it (N=6). A small number did not wish to disclose their ASD to their PCP (N=4), had privacy concerns (N=2), didn't like the report (N=1) or worried that their PCP would not react well to it (N=2). We were able to send AHAT reports to 88 PCPs, 41 (47%) of whom completed the survey. Most of the PCPs surveyed read the AHAT (97%), rated it as moderately or very useful (82%), and would recommend it to other patients (87%).

In pre-post intervention comparisons, the mean number of barriers decreased significantly (4.07 to 2.82, p<0.0001, effect size -0.55). For the 43 participants who saw their PCP during the one month follow-up period, satisfaction with PCP communication improved significantly (mean 30.9 to 32.6, p=0.03, effect size 0.26). Of note, we also found small but significant increases (mean 37.9 to 39.4, p=0.02, effect size 0.12) in a 21-item scale that we created de novo to capture potential toolkit-specific changes in patients' confidence in healthcare. While the scale had demonstrated strong internal consistency (alpha 0.92), additional work is needed to refine this scale and better target it to the toolkit's potential mechanisms of action.

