Patient Survey: All patient participants will be asked to take surveys at baseline and at six months. After logging into their secure account, participants complete surveys online (independently or with help from a supporter) using our Audio Computer Assisted Survey Instrument (ACASI), a highly accessible system with a read-aloud option and other features designed to meet the needs of people with disabilities. ⁴⁶ Participants without Internet access can take the survey at their primary care clinic or the PSU or Kaiser research offices.

After completing the baseline survey, participants from intervention sites will be automatically directed to use the AHAT to create a personalized report. After reviewing the report, they will be asked permission to have the report sent directly to their PCP. Participants will then be directed to the remainder of the toolkit (on a password-protected research site), where they can read information about health and healthcare and download worksheets and checklists. The research version of the toolkit will be accessible through participants' personal accounts to better track participants' use of components of the toolkit. Clinics will be expected to use the implementation protocol they developed to ensure the AHAT report reaches appropriate staff and that recommended strategies and accommodations are incorporated into the patient's care. Six months later, all participants will be re-contacted and asked to participate in the follow-up assessment. To increase retention, we will collect various types of contact information and will request permission to use updated information from clinical records, if needed. Participants will receive \$30 for completing both surveys.

We will collect data on patient provider communication using items we previously adapted⁶ from 2007 Health Information National Trends Survey (HINTS).⁴⁷⁻⁵⁰ We clarified wording and added two new items on expressive and receptive comprehension as community partners felt this was not adequately addressed in the initial scale. The scale asks patients about their last visit with their PCP. Responses use a 4-point Likert scale with anchors of "Never" to "Always". The scale is scored by summing the responses. In the post-test, participants will only be asked this scale if they have seen their PCP during the 6-month study. The original HINTS patient-provider communication scale and our adapted version both had a Cronbach's alpha of >=0.9.^{6,51}

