In cases where patients cannot participate directly, even with appropriate accommodations and supports, we will ask a supporter to participate as a proxy with as much input as possible from the patient. Supporters must also be age 18 and older, must speak (or read) English, and must have experience supporting the patient in healthcare settings. We expect to screen up to 500 participants to obtain an initial sample of 250 participants, with complete 6-month data for 200 participants. We will purposely sample 30 of these participants to take part in the qualitative interviews.

2) Primary Care Providers: We will include all primary care providers who practice in the intervention clinics. PCPs, by definition, are over 18 and speak English. They typically have MD, DO, NP, or PA degrees and practice primary care. We expect approximately 75 PCPs to take part in the survey. We will purposefully sample 15 of these PCPs to take part in the qualitative interviews.

3) Support staff: We will include an additional 15 clinic employees in the qualitative interviews. Employees will include front office staff (e.g. receptionists), back office staff such as medical assistants or nurses, and administrators (e.g. clinic managers). Again, by definition, they will be over age 18 and speak English.

Sampling plan

We will attempt to enroll all patients, age 18 or over, who have medical diagnoses of autism spectrum disorder, and are receiving primary care in the participating sites. We also will attempt to survey all primary care providers who have autistic adults on their panels in each clinic. We will work with clinic champions from each clinic to purposefully select which additional employees to invite to the qualitative study.

1b. Sources of Materials

Data will come from surveys, semi-structured open-ended interviews, and review of exiting data available in the patients' electronic medical records (EMR).

Survey data will be collected from patient participants or supporters via an Audio-Computer Assisted Self-Interview (ACASI). A-CASI is a secure, web-based, and highly accessible tool that offers participants additional privacy by allowing them to enter data themselves. The ACASI electronic database is stored behind the PSU firewall. It will be password-protected and only the PI and specific PI-designees will have access to participant information.

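### The stated 97% power at an effect size of 0.5 does not follow from the plan's own inputs, which give 94%

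*Combined protocol and SAP*

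**What the plan says.** The inputs are in the Power Considerations paragraph, under Quantitative Data Analysis. The plan is to enrol 250 participants and obtain "complete follow-up data on at least 200 (100 intervention;100 control"). The calculation uses an "independent sample t-test test with a two-tailed hypothesis and an alpha of 0.05". On that basis the paragraph gives 80% power for a standardised effect of 0.4. The next sentence reads: "It would provide 97% power to detect an effect size of 0.5". It names no new sample size, test or alpha, so it inherits those just given.

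The same paragraph then supports the expected effect with the earlier single-arm evaluation: "we noted a 0.55 effect size in the number of barriers to healthcare". The patient entry under Participant Characteristics / Inclusion Criteria repeats the numbers, with an "initial sample of 250 participants, with complete 6-month data for 200 participants". No other section offers different inputs for the 97%.

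**The concern.** Two power figures stand side by side and should come from one calculation, differing only in effect size. A method that returns 80% at 0.4 should return its matching value at 0.5, and 97% is too high for that. A gap of three points is more than rounding or a choice between the normal and the t formula can explain.

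This is the plan's only power statement for the Aim 2 outcomes, and the reader cannot tell whether the power or the effect size is the wrong number. The study is also meant to inform power estimates for the later cluster-randomised trial, so a figure that cannot be reproduced should not be carried forward.

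**Working it through.** **Inputs** (all from Power Considerations): n = 100 per arm, two-sided alpha = 0.05, independent-samples t-test, effect size d in standard deviation units.

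**Formula.** Degrees of freedom are 2n − 2 = 198. The noncentrality parameter is d × √(n/2) = d × √50 = d × 7.071. Power is the probability that a noncentral t variable with this parameter falls outside ±1.972, the two-sided 5% critical value. As a check, the normal approximation is Φ(d√50 − 1.960).

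**The plan's first figure, d = 0.4.** The noncentrality is 0.4 × 7.071 = 2.828. Power is 80.4% (normal approximation 80.7%). The stated 80% reproduces.

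**The plan's second figure, d = 0.5.** The noncentrality is 0.5 × 7.071 = 3.536. Power is 94.0% (normal approximation 94.2%; 94.0% in a simulation of 200,000 trials). The stated 97% does not reproduce.

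**Can one sample size give both figures?** Two-sided power by completers per arm:

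| n per arm | d = 0.4 | d = 0.5 |
|---|---|---|
| 98 | 79.6% | 93.6% |
| 100 | 80.4% | 94.0% |
| 101 | 80.8% | 94.2% |
| 114 | 85.2% | 96.4% |
| 115 | 85.6% | 96.5% |
| 119 | 86.7% | 97.0% |
| 123 | 87.8% | 97.4% |
| 124 | 88.0% | 97.5% |

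Power at 0.4 rounds to 80% only for 98 to 100 per arm. Power at 0.5 rounds to 97% only for 115 to 123 per arm (at 124 it is 97.51%, which rounds to 98%). The two ranges do not overlap.

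**Other routes to 97%:**

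| Change to the stated inputs | d = 0.4 | d = 0.5 | Conflict with the text |
|---|---|---|---|
| One-sided test, 100 per arm | 88.0% | 97.0% | The text says two-tailed; the 80% no longer holds |
| All 250 enrolled, 125 per arm | 88.3% | 97.6% | The text uses completers; the 80% no longer holds; 97.6% rounds to 98% |
| 200 completers split 90/110 | 80.0% | 93.8% | Power falls |
| 200 completers split 80/120 | 78.8% | 93.2% | Power falls |

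With 100 per arm and the two-sided test kept, an effect size of 0.55 gives 97.2% (noncentrality 0.55 × 7.071 = 3.889). That is the pilot value quoted in the same paragraph, and it leaves the 80% at 0.4 intact, but the sentence says 0.5. With 100 per arm, power rounds to 97% only for effect sizes of about 0.536 to 0.557.

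**The case against.** The strongest objection concerns weight, not arithmetic. The 97% is a secondary remark: the sample size rests on 80% power at 0.4, which reproduces, and no analysis uses the 97%. The study is a non-randomised pilot whose findings are meant to refine later power estimates, so moving from 97% to 94% changes no decision. That stands, and the point should be read as a correction of one number.

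The completer target is also worded as a minimum. If the 80% is read as a floor, 115 to 123 per arm would satisfy both figures. But the paragraph gives 100 in each arm explicitly, and at 100 the second figure fails.

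A fair point of wording is that the pair (0.5, 97%) is what is inconsistent, and the documents do not establish which member is wrong. Nor is the 119 per arm needed for 97% a shortfall, since the plan never sets 97% as a target.

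Finally, a label saying what the figure is not goes beyond the arithmetic. The paragraph already names the t-test and says that its estimate is conservative in view of the multivariate analyses. The label is accurate and useful, but the correction does not depend on it.

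**Conclusion.** The concern holds. Under the stated design, power at an effect size of 0.5 is 94.0%. Taking the effect size as written, power is overstated by 97 − 94 = 3 percentage points, and the type II error is 6.0% instead of 3%. Reaching 97% at 0.5 would take 119 completers per arm, 238 in total, against the planned 200.

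The result needs no assumption beyond the plan's own inputs and those of the t-test itself: independent observations, equal variances and equal arms. Which slip produced the 97% cannot be determined from the documents. The consequence is minor: the sample size justification stands, and 94% remains high power.

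**What to change.** In Power Considerations, change 97% to 94% for an effect size of 0.5. If another input was meant, such as a different effect size, state it and give the power that goes with it.

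It is worth adding a short label that both power figures refer to the stated two-tailed t-test with 200 independent completers who have the outcome measured. They are not the power of the planned "a mixed effects regression analysis to compare results from intervention and control sites". Nor do they apply directly to the communication outcome, because at follow-up "participants will only be asked this scale if they have seen their PCP during the 6-month study", so fewer than 200 may contribute.

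The cost is one number and one clause. This correction leaves the sample size, test and analysis unchanged.

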Preliminary analyses will include careful examination of descriptive statistics and distribution for each of the study variables at baseline and the 6-month follow-up. This will include stratified analyses within the intervention and control groups. For variables measured with multiple items, psychometric analyses (Cronbach's alpha, confirmatory factor analysis) will be conducted to instigate internal reliability, and, when necessary, measurement modifications will be made to improve reliability.

We will use two independent sample T-tests to test bivariate differences between the main independent variable (intervention vs control clinic) and baseline continuous variable subject characteristics and Chisquare/Fisher-Exact test to assess differences between the main independent variable and categorical variables. We will apply similar tests to primary outcomes and secondary outcomes at each time point.

We will test Aim 2 hypotheses using multivariate regression models. The dependent variable in each of our primary analyses will be the 6-month change in short-term outcomes (patient-provider communication score and number of barriers). We will calculate change by subtracting the baseline score from the score at 6 months. We will also conduct exploratory analyses using the 6-month change in scores for the potential

mechanisms of action (e.g., self-efficacy, use of accommodations) and long-term outcomes (e.g., unmet needs, emergency department use) as the dependent variable. Analyses will use linear vs logistic models depending on whether the outcome is continuous (e.g., patient-provider communication score) or binary (e.g., ED use, unmet needs). The predictor will be study arm (intervention vs control). We will adjust for potential confounders including data source (direct report vs proxy), age, gender, race/ethnicity, residence (own home vs with family of origin); need for support to communicate with providers; health status, and unmet needs at baseline.

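### The pilot results cited for an expected effect of 0.4 to 0.5 support it for the barriers count only; for communication, the other primary outcome, the pilot effect was 0.26, and the planned sample gives about 45% to 67% power

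*Combined protocol and SAP*

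**What the plan says.** Under Quantitative Data Analysis, the dependent variables of the primary analyses are the 6-month changes in the "short-term outcomes (patient-provider communication score and number of barriers").

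Power Considerations sets a single target for both. The sponsor wants "complete follow-up data on at least 200 (100 intervention;100 control"), to "detect an effect size of 0.4 with a power of 80" per cent, "using an independent sample t-test test with a two-tailed hypothesis and an alpha of 0.05". A second figure is given for an effect of 0.5. After a general caution about taking effect sizes from small pilots, the text appeals to the preliminary results and says "we feel it is reasonable to expect this level of change in our short-term outcomes". The support is one sentence: "For example, we noted a 0.55 effect size in the number of barriers to healthcare". The section then calls its estimate conservative, to allow for the multivariate analyses. It gives no effect size for communication.

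That effect size appears earlier, under Evaluation of the Healthcare Toolkit. Among the 43 participants who saw their PCP in the one-month follow-up, "satisfaction with PCP communication improved significantly (mean 30.9 to 32.6, p=0.03, effect size 0.26"). The pilot had a single arm and no controls.

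**The concern.** The expectation is stated for the short-term outcomes together, but the evidence shown is for one of them. The pilot value for the other is 0.26, about two thirds of 0.4 (0.26 / 0.4 = 0.65). The claim to be conservative fits barriers, where 0.4 lies below 0.55. It does not fit communication, where 0.4 lies above 0.26.

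A reader of Power Considerations alone would take 80% as the power that the sponsor's evidence supports for both primary outcomes. Aim 2 states a directional hypothesis for each, and Anticipated Difficulties and Next Steps says that the findings will be used to refine outcome measures and power estimations for the larger trial. A non-significant communication result is easier to interpret if the plan says beforehand how much power its own pilot implied.

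**Working it through.** **Inputs.** From Power Considerations: 100 per arm, two-sided alpha 0.05, independent-samples t-test. From Evaluation of the Healthcare Toolkit: communication mean 30.9 to 32.6 (change 1.7), n = 43, p = 0.03, effect size 0.26; barriers effect size 0.55 in absolute value.

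**Formula.** For standardised effect d and n per arm, the noncentrality is d × √(n/2) on 2n − 2 degrees of freedom. Power is the probability that this noncentral t falls beyond ± the critical value, which is 1.972 for n = 100.

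**Step 1: the plan's own figure.** At d = 0.4: 0.4 × √50 = 2.83, power 80.4%. The stated 80% reproduces. The smallest effect detectable with 80% power is 0.398, so there is no slack below 0.4.

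**Step 2: the two pilot effects in the same design.**

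| Outcome | Pilot effect | Noncentrality | Power at 100 per arm |
|---|---|---|---|
| Barriers | 0.55 | 3.89 | 97% |
| Communication | 0.26 | 1.84 | 45% |

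**Step 3: the scale of the 0.26.** The primary analysis uses change scores, so the relevant standardiser is the standard deviation (SD) of change. The plan does not say which SD was used in the pilot.

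- The 0.26 implies an SD of 1.7 / 0.26 = 6.5.
- If 0.26 were already in change-SD units, a paired t would be 0.26 × √43 = 1.70, giving p of about 0.10 rather than 0.03. Under a paired t-test, then, 0.26 was scaled by some other SD.
- Assume that p = 0.03 is from a paired t-test. Then t on 42 degrees of freedom is 2.246, the SD of change is 1.7 × √43 / 2.246 = 4.96, and the effect is 1.7 / 4.96 = 0.34.
- At 0.34 with 100 per arm, power is 67%. If the true p lay anywhere from 0.035 to 0.025 before rounding, the effect is 0.33 to 0.35 and power 65% to 70%.

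The change-SD scale matches the endpoint better and narrows the gap, but power stays below 80%.

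**Step 4: who answers the scale.** Under Patient Survey, the follow-up communication scale is asked only of participants who saw their PCP during the six months. The documents give no visit rate, so the numbers per arm below are assumptions.

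| Respondents per arm (assumed) | Power at 0.26 | Power at 0.34 |
|---|---|---|
| 100 | 45% | 67% |
| 90 | 41% | 62% |
| 75 | 35% | 54% |
| 50 | 25% | 39% |

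The figures in Steps 2 and 3 are therefore upper ones if fewer than 100 per arm respond.

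**Step 5: precision of the pilot.** Under the same paired assumption, the approximate 95% confidence interval for the change-SD effect of 0.34 is 0.03 to 0.65. It contains 0.4.

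**The case against.** The strongest reply is that the pilot does not contradict 0.4. It had 43 respondents, the interval is wide, the 0.26 is reported openly elsewhere in the document, and Power Considerations itself warns about small pilots. All of that stands. But a general caution does not tell the reader that one primary outcome had a much smaller pilot effect than the one quoted.

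A second reply is that this trial may do better than the pilot. The Significance section says that the toolkit's utility was probably reduced because it was not built into clinic work-flow; here it will be, and follow-up is six months rather than one. Against that, a comparison with control clinics removes whatever change those clinics show. The net direction is unknown. Power Considerations argues neither side and relies on the preliminary results.

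Three stronger readings are tempting and should not be drawn:

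- *That the trial would more likely than not miss a communication effect.* This holds at 0.26 (55% chance of missing it). With 100 per arm it does not hold at 0.34, where detection is the likelier result.
- *That 0.26 is inflated because it comes from people who saw their PCP.* The trial restricts its follow-up scale in the same way. The restriction can reduce numbers, but it does not show inflation.
- *That a null result would remove communication from the larger trial.* No section says so. Next Steps speaks of refining outcome measures, and the outcomes that Aim 4 says will be chosen are long-term utilization outcomes.

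**Conclusion.** The point holds as a mismatch between a stated expectation and the evidence given for it. The preliminary results support 0.4 to 0.5 for the barriers count, subject to the limits of a single-arm, one-month comparison. They do not support it as the expected value for communication. On the plan's inputs, power for communication is about 45% at the reported 0.26, or about 67% (65% to 70%) at about 0.34 in change-SD units, against the stated 80% at 0.4.

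The 67% rests on p = 0.03 coming from a paired t-test. Both figures take the pilot change as the between-arm difference and assume 100 communication respondents per arm. The documents do not support saying that 0.4 is wrong or unattainable for communication, only that the cited pilot is not a basis for expecting it.

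**What to change.** In Power Considerations:

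1. Limit the pilot-based support for 0.4 to the barriers count.
2. State the communication pilot effect: 0.26 as reported, about 0.34 in change-SD units if the p-value was from a paired t-test (the sponsor can confirm this from the pilot data). Give the corresponding power at 100 per arm, about 45% to 67%, and say that it falls if fewer participants have a PCP visit.
3. Note that both pilot values are single-arm, one-month changes. If the sponsor expects integration and longer follow-up to raise the communication effect, say so there as an argument separate from the pilot.
4. State that the communication result will be interpreted from its estimate and confidence interval.

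This is wording only. It adds no patients, changes no design feature, and needs no rule about keeping the endpoint in the later trial. The cost is a less favourable stated power for one of the two primary outcomes.
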